3.13.3 Demographic and clinical characteristics of SARI

Demographic and clinical characteristics of the SARI patients will be provided, overall and by SARIcausing pathogen (type and/or subtype), including age groups, gender, symptoms, presence of chronic conditions, BMI, vaccination status, having had preventive monoclonal antibodies, pregnancy, smoking history, use of antiviral or virus-specific monoclonal antibody therapy, long-term care facility residence, and healthcare utilisation outcomes. Overall clinical characteristics will also be provided stratified by calendar month of disease-onset.

3.13.4 Healthcare utilisation outcomes

Multinomial logistic regression will be used to explore risk factors of pathogen-specific SARI hospitalisation, healthcare utilisation outcomes (as defined in Section 3.6.5), and the presence of co-infections (by number of co-infections and involved pathogens, when feasible). Potential risk factors include age, gender, chronic conditions, smoking). Stratified analyses will be performed by age groups, by gender, by presence of chronic condition and specifically by those with pre-existing immunodeficiency disorders.

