Variables that will be collected include age, gender, history of medical diagnosis for selected morbidities of interest (chronic pulmonary disease (e.g., asthma, chronic obstructive pulmonary disease (COPD), emphysema), cardiovascular disease, hypertension, chronic liver disease, chronic renal disease, type 1 and type 2 diabetes, cancer, immunodeficiency disorders, obesity, and neurological disorders), body mass index (BMI), smoking history, previous SARS-CoV-2 infection, prior SARI hospitalisation and time since hospitalisation, vaccination against respiratory pathogens (SARS-CoV-2, influenza, RSV, pneumococcus; including brand and date of vaccination), calendar time, pregnancy (and term), respiratory support, intensive care unit (ICU) stay, in-hospital death, any use of preventive or therapeutic antivirals or virus-specific monoclonal antibodies prior or during hospitalisation, long-term care facility residence, and discharge destination.

Data collection

After study enrolment, data will be collected from primary (e.g., lab results) and secondary data sources (e.g., vaccination registries). Information to be collected at minimum include:

- SARI symptoms and onset date;
- date of sampling, outcome of specimen testing, assay used;
- date of hospital admission and discharge;
- Healthcare utilisation outcomes (in-hospital death, ICU admission, respiratory support, discharge destination, length of stay);
- covariates, including vaccination details (see Covariates section).

Exposure status, brand information and date of vaccination(s) will be ascertained by consulting vaccination registries, vaccination cards or medical records (depending on the country and region). Where needed, treating physician or other health care professionals will be contacted to obtain additional information.

Statistical analysis

Clinical characteristics of the SARI patients will be provided, overall and by SARI-causing pathogen (type and/or subtype), including age groups, gender, symptoms, presence of chronic conditions, BMI, vaccination status, receipt of preventive monoclonal antibodies, pregnancy, smoking history, use of antiviral or virus-specific monoclonal antibody therapy, long-term care facility residence, and healthcare utilisation outcomes. Overall clinical characteristics will also be provided over time (monthly).

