3.3 Study population

The study population consists of adults aged 18 years and older (patients), presenting at the participating hospitals during the study period, who

- meet the inclusion criteria (see Section 3.3.1) AND
- are hospitalised and meet the SARI case definition (see Section 3.6.2).

Participants may be co-enrolled in interventional trials. The name of the trial will be collected, to allow for exclusion from specific analysis, where required, and will be prespecified in the statistical analysis plan (SAP).

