3.6.3 Laboratory-confirmed infection

For each studied pathogen, a laboratory-confirmed infection is a positive reverse transcription polymerase chain reaction (RT-PCR)³ or multiplex RT-PCR on a respiratory specimen(s) collected between 14 days prior to and up to 72 hours after hospital admission. If all samples collected in this time frame are negative, the patient is considered as not having any laboratory-confirmed infection.

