3.6.4 Laboratory-confirmed co-infection

Laboratory-confirmed co-infection is defined as two or more laboratory-confirmed infections (Section 3.6.3) on any respiratory sample taken in the accepted timeframe (collected between 14 days prior to and up to 72 hours after hospital admission).

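### The pathogen regression cannot estimate risk factors for hospitalisation in an all-hospitalised sample, and its outcome classes overlap

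*Protocol*

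**What the plan says.** Section 3.13.4 of the protocol, repeated in the abstract under Statistical analysis, names one method for three families of outcome: "Multinomial logistic regression will be used to explore risk factors of pathogen-specific SARI hospitalisation, healthcare utilisation outcomes (as defined in Section 3.6.5", followed by "the presence of co-infections (by number of co-infections and involved pathogens, when feasible". On covariates it says: "Potential risk factors include age, gender, chronic conditions, smoking". No reference category and no coding rule for co-infected patients is given.

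Section 3.3 limits the study population to adults who "are hospitalised and meet the SARI case definition". Section 3.6.3 sets infection pathogen by pathogen: "For each studied pathogen, a laboratory-confirmed infection is a positive reverse transcription polymerase chain reaction". Section 3.6.4 adds: "Laboratory-confirmed co-infection is defined as two or more laboratory-confirmed infections". Sections 3.8.1 and 3.8.2 make only SARS-CoV-2, influenza and RSV testing mandatory. Table 2 lists panels from 4 to 21 targets, several still to be confirmed, and its footnote says that one Italian location does not yet use multiplex testing.

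Section 5 states that the catchment denominators are too coarse for incidence by chronic condition. It says the data can instead compare the share of patients with a condition between pathogens.

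**The concern.** Two features of the planned model do not fit the design.

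First, a risk factor for hospitalisation needs a comparison with people who were not hospitalised, and the regression has none. Catchment populations enter only the incidence calculation in Section 3.13.5. The model therefore compares one kind of SARI admission with another. A reader who takes its odds ratios as risks of being hospitalised could conclude that a condition is harmless, or even protective, because it raises the risk of all SARI by a similar amount.

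Second, a multinomial outcome needs mutually exclusive classes. Under Sections 3.6.3 and 3.6.4 a patient with RSV and influenza belongs to both pathogen groups, and co-infection is itself the secondary objective. With unequal panels, whether a patient has one pathogen, several or none cannot always be known.

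**Working it through.** **1. The plan's own figures.** Section 3.10: 300 patients × 22 hospitals = 6,600, and 6,600 × 0.90 = 5,940, as stated. The Table 4 precisions reproduce as half-widths of exact 95% binomial intervals at n = 5,940 (for example RSV 2%: 0.365%; RSV 7%: 0.657%). Section 3.10 gives no figure for the regression models.

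**2. What the model estimates.** Let RR_X be the factor's population risk ratio for hospitalisation with pathogen X, and RR_C its risk ratio for the comparator SARI admissions. If enrolment and testing do not depend on the factor, the odds ratio within SARI admissions is RR_X / RR_C. With an illustrative RR_X = 3:

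| RR_C | Odds ratio within SARI |
|---|---|
| 1 | 3/1 = 3.0 |
| 2 | 3/2 = 1.5 |
| 3 | 3/3 = 1.0 |
| 4 | 3/4 = 0.75 |

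A factor that raises all SARI equally shows no effect, and one that raises other SARI more appears protective. No choice of adjustment variables changes this.

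**3. Size of the overlap.** Inputs are the Table 4 prevalences: SARS-CoV-2 20–25%, RSV 2–7%, influenza 7–12%. Independence between infections is an assumption; the protocol gives no co-infection rate.

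- Minimum: P(none) = 0.80 × 0.98 × 0.93 = 0.7291 and P(exactly one) = 0.2520. So P(two or more) = 0.0188, about 112 of 5,940.
- Maximum: P(none) = 0.75 × 0.93 × 0.88 = 0.6138 and P(exactly one) = 0.3345. So P(two or more) = 0.0517, about 307 of 5,940.
- RSV-positive patients who also carry SARS-CoV-2 or influenza: 1 − 0.80 × 0.93 = 25.6% at the minimum and 1 − 0.75 × 0.88 = 34.0% at the maximum.

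Over all patients the overlap is modest, at 1.9% to 5.2%. Within the RSV group it is a quarter to a third. Coding the outcome as none, single pathogen or co-infection would move those patients out of the RSV class, which would then mean RSV alone. That is not how Section 3.6.3 defines an RSV infection, nor how the second primary objective groups patients.

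**4. Panels.** A patient tested only for the core viruses and positive for one of them may or may not carry a further pathogen. A patient negative on all of them may carry one that was not sought. Neither can be placed in an exclusive class across the full pathogen list. How many such patients there will be cannot be derived: the contributors with a listed 4-target assay also list larger panels, and Table 2 does not say who receives which.

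**5. Calendar time and site.** Take 3,000 winter and 2,940 summer patients, RSV at 8% and 0.5%, and no true age effect within either season. All of these are assumptions apart from the total.

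- 60% versus 45% elderly. Elderly: 144 + 6.6 = 150.6 RSV-positive, 2,972.4 negative. Younger: 96 + 8.1 = 104.1 positive, 2,712.9 negative. Crude OR = (150.6 × 2,712.9) / (104.1 × 2,972.4) = 1.32.
- 55% versus 50% elderly: (139.35 × 2,704.65) / (115.35 × 2,980.65) = 1.10.
- Equal age mix: 1.00.

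The bias depends on the age split, about which the protocol gives no figures.

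**The case against.** The strongest reply is that Section 3.13.4 is an outline and Section 3.13 leaves full specification to the SAP. The SAP could define exclusive classes, and the same sentence already treats co-infection as an outcome of its own. This stands against any inference that co-infected patients must be dropped or classed arbitrarily. It does not remove the point, because exclusive coding changes the question for a sizeable part of the RSV group and does not settle the class of patients tested on a short panel.

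On the target, the protocol speaks only of exploring, the objective served is to characterise SARI patients, and Section 5 describes the between-pathogen comparison correctly. That limits the harm. It also shows that Section 3.13.4 names a quantity that the rest of the protocol does not claim to deliver.

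A reader might infer from the listed covariates that the model will contain no site or calendar-time terms and will therefore be confounded. The text does not support this. The list is introduced as potential risk factors and is open. Calendar time is among the collected variables in the abstract ("calendar time, pregnancy (and term), respiratory support"), and both calendar time and Study Contributor stratify the results in Section 3.13.2. Adjustment sets are ordinary SAP content.

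A sparse-data argument is likewise not established. At 2% RSV there are 0.02 × 5,940 = 119 cases, but at 7% there are 416, and the number of model terms depends on coding that the protocol does not fix.

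**Conclusion.** The point holds for the named target and for the form of the outcome. The target is misnamed whatever the SAP says, because everyone analysed is a hospitalised SARI patient. The possible distortion runs from none to a reversed direction (3.0 to 0.75 in the illustration), depending on how the factor acts on other SARI.

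A single multinomial pathogen outcome fits poorly with per-pathogen definitions and unequal panels. The overlap would be 1.9% to 5.2% of all patients and 26% to 34% of RSV-positive patients, on the Table 4 prevalences and assumed independence; the true overlap may differ.

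Confounding by month or site is plausible, since Table 1 shows different recruitment wards, Table 2 different assays, and a Table 3 footnote one contributor that excludes long-term care residents. It is not demonstrated, and the silence on adjustment is not a finding in itself.

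**What to change.** Reword Section 3.13.4 and the matching abstract text as follows.

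- Name the target *factors associated with detection of pathogen X among hospitalised SARI patients*.
- Fit one binary logistic model per pathogen, comparing patients positive for it with those tested and negative for it. A co-infected patient then counts as positive in each relevant model, and a patient not tested for a pathogen is left out of that model only.
- Keep multinomial or ordinal models for the mutually exclusive severity and respiratory-support classes of Section 3.6.5.1.
- Preferably state that calendar time and site enter the pathogen models as adjustment terms, since pathogen mix and case mix may both vary by month and site.

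The cost is several models instead of one, with different numbers of patients where panels differ. No new data are needed: calendar time, contributor, assay and per-pathogen results are already recorded or known.

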3.13.5 Incidence rates

As part of the exploratory objectives, pathogen-specific SARI incidence rates (per 100,000 personyears) will be calculated and monitored over time to identify trends using the following formula [27]:

 $Incidence \ rate = \frac{\text{Number of events in specified period}}{\text{Average number of persons at risk during the same specified period}}$

The number of events in a specific period will be calculated by multiplying the percentage of SARI patients testing positive for a specific pathogen within the selected time period with the total number of SARI patients (included in the Surveillance Study and missed SARI patients identified by screening logs). Alternatively, the untested SARI events may be accounted for by multiple imputation of expected testing results (e.g., for RSV [2, 3]).

Incidence estimates will not be calculated unless formal denominator mapping can be performed and there is an accurate process for identifying SARI events that were missed by active surveillance. Denominator data will be based on the hospital-reported catchment population of each hospital. The

Confidential Version 1.0 21 March 2024 Page **35** of **49** total number of hospital beds in a region corresponding to the Study Contributor's catchment region will be obtained, and the percentage of hospital beds caught by the specific Study Contributor will be calculated. The percentage of hospital beds caught by the Study Contributor will be used to calculate the hospital's catchment population. The catchment population of each hospital is expected to reflect the average number of persons at risk during that same time period Official regional (or national if not available) population gender- and age-specific distributions will be obtained to model these characteristics for the Study Contributor-specific catchment populations. These modelled data will be used to calculate gender- and age-specific incidence rates of SARI by pathogen. Further, incidence rates will also be adjusted for events missed due to lower diagnostic testing sensitivity of single specimens among older adults as seen in several recent incidence meta-analyses [28, 18]. Details will be provided in the SAP.

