The total number of laboratory samples and proportion positive for each respiratory pathogen of interest and co-infections will be provided. Counts and proportions, along with 95% exact binomial confidence intervals, will be provided by calendar time, by Study Contributor, by country, and by age- and risk groups of interest. Co-infections will be described, by number of pathogens, by pathogen type and by healthcare utilization outcome.

Multinomial logistic regression will be used to explore the risk factors of pathogen-specific SARI hospitalisation, healthcare utilisation outcomes, and the presence of co-infections (by number of co-infections and involved pathogens, when feasible). Potential risk factors include age, gender, chronic conditions, and smoking. Stratified analyses will be performed by age groups, by gender, by presence of chronic conditions and specifically by those with pre-existing immunodeficiency disorders.

Pathogen-specific SARI incidence (per 100,000 person-years) will be derived from the percent pathogen positivity and the estimated catchment populations of the hospitals, if appropriate denominator data and comprehensive SARI surveillance to identify untested SARI events are both available. The feasibility of obtaining appropriate catchment population data and a complete SARI numerator will be assessed by site. If feasible, pathogen-specific SARI incidence will be calculated by calendar time, by Study Contributor, by country, and by age groups. Time trends will be explored treating calendar time as a categorical variable and as a continuous variable using penalised smoothing splines.

Reporting

Progress reports will be provided every two months from enrolment of the first participant. Progress reports will provide recruitment numbers, main demographic and clinical characteristics of SARI patients and pathogens detected. Study reports will be prepared once a year, covering the primary and secondary objectives. A final report will be prepared after 12 months of data collection.

Feasibility assessments for future respiratory disease effectiveness studies will be detailed in study feasibility reports and will be performed at the latest 12 months after start of the study data collection. Additional feasibility reports can be triggered (e.g., to evaluate any modifications to improve data quality, or upon major changes to the respiratory pathogen- and vaccine landscape).

Data management

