4.3 Monitoring

Monitoring activities include:

- Before study start, the Study Contributor will be asked to complete a quality management questionnaire to inform the Study Team on all aspects of the study conduct.
- Before study start, a site initiation visit will be organised by the Study Team.
- During study conduct, regular Study Contributor contacts will be organised to monitor study progress (number of patients enrolled), to ensure regular data input to the id.DRIVE electronic data capture (EDC) system and to discuss potential protocol deviations or other issues related to the study conduct.

- Sites will be asked to keep high-level screening logs (including number of SARI patients missed or not consented for the study with age group and gender), as they may affect interpretation of trend data.
- Monitoring shall occur as described in the id.DRIVE Monitoring Plan.

The Study Contributor investigators must permit any external auditor mandated by the QAAC of the id.DRIVE partnership or the Study Requestor, the IEC, auditors and representatives from regulatory authorities direct access to all study-related documents. Efforts will be made to maintain participant confidentiality at all times.

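### The incidence formula in Section 3.13.5 divides by a headcount with no time term, so it does not give the stated rate per 100,000 person-years unless the period is exactly one year

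*Protocol*

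**What the plan says.** Section 3.13.5 (Incidence rates) states that "pathogen-specific SARI incidence rates (per 100,000 personyears) will be calculated and monitored over time". The formula printed beneath has "Number of events in specified period" as its numerator and "Average number of persons at risk during the same specified period" as its denominator. The same section then says where the denominator comes from: each hospital's catchment population, estimated from its share of regional hospital beds, is taken to represent the average number at risk. That is a count of people.

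The Statistical analysis part of the abstract uses the same unit: "Pathogen-specific SARI incidence (per 100,000 person-years) will be derived from the percent pathogen positivity and the estimated catchment populations of the hospitals". It also sets out the breakdown, provided the data allow it: "pathogen-specific SARI incidence will be calculated by calendar time, by Study Contributor, by country, and by age groups". Calendar time is to be examined both in categories and as a smooth function.

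On duration, the Milestones table runs data collection from June 2024 to May 2025. Section 3.4 gives a minimum of 12 months and an expected two years.

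**The concern.** A rate per person-year needs person-time in its denominator. The printed formula has persons only, so its result depends on the length of the period chosen, while the label stays the same whatever that length is. Formula and unit therefore disagree.

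This matters because the rates are meant to be followed over time. Within 12 months of data collection, a time trend in incidence can be shown only by using periods shorter than a year, and those are the periods for which the formula and the label part. An analyst who programmes the formula as printed would produce sub-annual figures that cannot be set beside an annual rate, or beside published person-year rates such as the influenza hospitalisation rate quoted in Section 1. An analyst who annualises because of the label would be departing from the printed formula. Both could claim to follow the protocol.

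**Working it through.** The protocol states no incidence figure, so there is none to reproduce. The check is one of units, followed by an illustration.

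**Inputs**
- Unit: per 100,000 person-years (Section 3.13.5 and abstract).
- Formula: events in the period divided by average persons at risk (Section 3.13.5).
- Illustrative constant rate: 437 per 100,000 person-years, the influenza hospitalisation rate for ages 65 and over quoted in Section 1.
- Catchment size P: not given. P = 1,000,000 is assumed; it cancels, so the choice does not affect the result.

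**Formulas**, with E the events and T the period length in years
- As printed: E / P × 100,000
- Person-time rate: E / (P × T) × 100,000
- Ratio of printed to person-time rate: T

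**Numbers.** At a constant rate, E = 0.00437 × 1,000,000 × T.

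| Period | T | Events E | Formula as printed | Person-time rate | Printed value is |
|---|---|---|---|---|---|
| One month | 1/12 | 364.2 | 36.4 | 437 | 12-fold too low |
| Two months | 1/6 | 728.3 | 72.8 | 437 | 6-fold too low |
| Six months | 1/2 | 2,185 | 218.5 | 437 | 2-fold too low |
| 12 months | 1 | 4,370 | 437 | 437 | correct |
| 24 months | 2 | 8,740 | 874 | 437 | 2-fold too high |

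For example, one month gives 364.2 / 1,000,000 × 100,000 = 36.4 as printed, and 364.2 / (1,000,000 × 1/12) × 100,000 = 437 with person-time.

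The discrepancy is T itself. It does not depend on the pathogen, the catchment or the true rate.

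**The case against.** The case for leaving the text alone has several parts.

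- **The label already calls for annualising.** The unit appears in both places, and a careful analyst would scale by it. That makes a wrong published figure less likely, but the printed formula and its stated unit still conflict.
- **The planned data collection is 12 months.** Over June 2024 to May 2025 the formula is numerically right, and Section 8.3 has study reports prepared yearly. No passage plans one pooled 24-month rate, so the 2-fold excess is a consequence of the formula and not a planned result. This stands.
- **Trends survive.** Periods of equal length all carry the same factor, so their relative pattern is unaffected. This stands too. The damage is to the level of the rates and to comparisons across periods of different length.
- **Incidence is exploratory and conditional.** It is calculated only with formal denominator mapping and an accurate way to find missed cases, and Section 5 says it is reported only once considered valid. This stands and limits the severity.
- **Details go to the SAP.** This does not answer the point. The protocol has itself printed a formula that disagrees with its unit; nothing here is merely left for later.

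A reader might go further and infer that the numerator is biased because positivity is pooled across strata with unequal enrolment. The numerator rule is "multiplying the percentage of SARI patients testing positive for a specific pathogen within the selected time period with the total number of SARI patients". It names the time period but does not say whether the product is formed overall or within site, age or gender. The section plans age- and gender-specific rates, offers multiple imputation as an alternative and defers details to the SAP. The 300 patients per hospital in Section 3.10 is anticipated recruitment, not a cap, so it does not show under-enrolment in winter. Nor can one conclude that the screening logs lack dates: Section 4.3 introduces "number of SARI patients missed or not consented for the study with age group and gender" as something the logs include, not as a full list of fields. The documents support neither a pooling error nor a size for one.

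**Conclusion.** The formula in Section 3.13.5 is wrong as written for its stated unit. It departs from a person-year rate by a factor equal to the period length in years: 12-fold too low for a month, 2-fold too low for six months, correct for 12 months, and 2-fold too high for a single two-year rate. These factors assume only that the formula is applied literally. The 437 serves as an illustration and the catchment size cancels.

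Severity is low. The objective is exploratory and subject to feasibility, no primary or secondary result depends on it, the 12-month figure is unaffected, and trends over equal periods are preserved. The conclusion concerns the denominator only.

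**What to change.** In Section 3.13.5, define the denominator as the average number of persons at risk multiplied by the length of the period in years, and state that the quotient is multiplied by 100,000. Adjust the catchment sentence to say that the catchment population supplies the average number at risk, which is then multiplied by the period length to give person-years. Use the same definition in the SAP.

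The cost is one phrase in the formula and a matching edit to one sentence. It needs no new data and leaves the 12-month rate unchanged.
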